STUDY PROTOCOL:

Bipolar transurethral enucleation (BipolEP) vs bipolar transurethral resection of the prostate: A prospective interventional multi-center randomized controlled trial

Apporved by the Salzburgs ethics committee on 13.12.2017 Approval Number: 415-E/2251/11-2017

Applicant/	[name]
Coordinating	Uniklinikum Salzburg, University Clinic for Urology and Andrology,
investigator	[name]
Title of trial	Bipolar transurethral enucleation (BipolEP) vs bipolar transurethral resection of the prostate: A prospective interventional multi-center randomized controlled trial
Medical condition	Lower urinary tract symptoms due to benign prostatic enlargement
Objective(s)	The primary objectives of this study is (i) to demonstrate that the I-PSS at 12 months shows non inferiority for enucleation. Our hypothesis is that enucleation and bipolar TURP might be comparable in improving LUTS. The secondary objectives is to show increased tissue resection per minute for the enucleation (superiority) (ii).
Intervention(s)	Experimental intervention: Bipolar transurethral enucleation of the prostate (BipolEP) Control intervention: Bipolar transurethral resection of the prostate (TURP) Follow-up per patient: Dysuria visual analogue scale (at 1 month) I-PSS, QOL, Qmax and PVR (at 1, 4 and 12 months) IIEF-15 and PSA (at 4 and 12 months) TRUS for prostate size at 4 months
Key inclusion and exclusion criteria	Age greater than 50 years Refractory LUTS secondary to BPH I-PSS greater than 15 QOL score 3 or greater Qmax less than 15 ml per second or patients with acute urinary retention secondary to BPH in whom trial of voiding failed Prostate size on preoperative TRUS of 40 to 150 ml Key exclusion criteria: Patients with neurological disorder Active urinary tract infection, active bladder or prostate cancer
Outcome(s)	Primary efficacy endpoints: • IPSS improvement at 12 months Key secondary endpoint(s): • Tissue resection per minute Assessment of safety: • Assessment of possible adverse events after applying BipoLEP and compare to TURP (e.g. bladder perforation, urethra stricture, incontinence). • Comparison of peri- and postoperative complications according to the classification of Clavien-Dindo

	Blood loss (hemoglobin prior and postoperative)
Trial type	Prospective, interventional, multi-centre, randomized trial
	Concept
	The study is designed as a comparison of two kinds of treatment: Group BipolEP: Bipolar transurethral enucleation of the prostate Group TURP: Bipolar transurethral resection of the prostate
	Two primary endpoints are chosen: (1): IPSS after 12 month [-] (2): Tissue resection [g/min]
	The use of a gate keeping approach makes it unnecessary to adjust the type I error. Primary endpoint (1) will be investigated by a non-inferiority approach (type I error = 5% one-sided), primary endpoint (2) by a superiority approach (type I error = 2.5% one-sided).
	Hypotheses:
	(1): H-0 ₁ : Compared to group TURP, IPSS after 12months in group BipoIEP is higher (non-inferiority range = 3) H-1 ₁ : Compared to group TURP, IPSS after 12months in group BipoIEP is not higher (non-inferiority range = 3)
	(2): H-0 ₂ : Compared to group TURP, tissue resection in group BipolEP is not increased H-1 ₂ : Compared to group TURP, tissue resection in group BipolEP is increased
Statistical	Statistical Methods:
analysis	Group Comparisons:
	Primary Endpoint (1): Data (if appropriate, in logarithmised version) will be checked for normal distribution (Kolmogorov-Smirnov with Lilliefors significance correction, type I error = 10%). Hypotheses (H-0 ₁ , H-1 ₁) will be investigated either by a parametric or by a non-parametric one-sided test of equivalence (equivalence range one-sided = 3; type I error = 5% one-sided).
	Primary Endpoint (2): Data (if appropriate, in logarithmised version) will be checked for normal distribution (Kolmogorov-Smirnov with Lilliefors significance correction, type I error = 10%). Hypotheses will be investigated either by the t-test for independent samples or by the Mann-Whitney U-test (type I error = 2.5% one-sided). Hypotheses (H-0 ₂ , H-1 ₂) will be tested only if H-0 ₁ hypothesis is rejected.
	Further Variables: All other variables will be analysed by usual parametric and non-parametric tests for univariate comparisons of independent samples.
	Two-sided 95% confidence intervals: For selected variables, two-sided 95% confidence intervals will be calculated.
	Type I error adjustment: No adjustment for the type I error will be made. Therefore – apart from hypotheses testing – the results of inferential statistics will be descriptive only.
	Sample Size Justification:

The following scenario was used for the sample size estimation concerning primary endpoint (1):

- Non-inferiority range = 3
- Type I error = 5% one-sided
- Type II error = 10%
- IPSS after 12 months in both groups (Mw ± SD) = 4 ± 4
- n (group BipolEP) / n (group TURP) = 1 / 1
- Parametric test

The result of the sample size estimation is a requirement of 31 cases per group. Assuming a drop-out rate of 20% and considering the possible need for a non-parametric test a total of 84 inclusions (n=42 / group) are chosen as the sample size of the study.

Analysis Populations:

Intent-to-treat (ITT) population: All subjects at whom the group-specific treatment (TURP, BipoIEP) at least has started will be included in the ITT population. All variables will be analysed.

Per-protocol (PP) population: All subjects without occurrence of any drop-out situation (all valid cases) will be included in the PP population. All variables will be analysed. The PP analysis is paramount.

Handling of Implausible Values and of Missing Values:

Implausible values have to be identified during the data management process in agreement with the clinical investigator. They will be converted into missing values.

Missing Values will be replaced only in the ITT population and only for the two primary endpoints. The replacements will be made according to the worst-case principle (use of the worst assessed value in the study).

Post-hoc Analyses:

Analyses of subgroups and other post-hoc analyses can be performed for cause. However, all statistical results will be only descriptive.

Interim Analyses:

A priori no interim analysis is intended.

Presentation of the Results (Descriptive Analysis, Graphs etc.):

Categorical variables will be presented using counts and percentages. Variables measured on ordinal scales will be presented using counts and percentages (where appropriate) or minimum, 25%-percentile, median, 75%-percentile and maximum and number of patients (where appropriate). Continuous variables will be presented using minimum, 25%-percentile, arithmetic mean, median, 75%-percentile, maximum, standard deviation and number of patients.

All results will be presented in the form of tables, selected results additionally in the form of graphs (bar charts, boxplots).

Allcation

For the allocation of treatment to subjects the minimization method will be used (manual see accompanying documents).

	Strata:
	prostate 60 to 80 ml / more than 80 ml
	catheterized / non-catheterized
	The minimization procedure will be applied centrally (by the coordinating centre).
	According to the allocation approach and the multicentre nature of the study minor deviations in defined group BipolEP / group TURP ratio of 1 / 1 cannot be excluded.
	First patient in to last patient out (months): 36
Trial duration	Duration of the entire trial (months): 36
	Recruitment period (months): 12
Participating	N = 2
centres	

Intervention scheme/ Trial flow

1. 1. The Medical Problem

Lower urinary tract symptoms (LUTS) caused by prostatic enlargement (benign prostatic hyperplasia, BPH) are a common problem in elderly men. It is well known that the incidence of LUTS is rising with age and there are reported incidence rates of 38 cases per 1000 man-years at the age of 75-79 years [1]. In the EAU guidelines LUTS is divided in three different groups, mild, moderate and severe, by using the international prostate symptoms score (IPSS). Surgical intervention is recommended for moderate to severe LUTS. However, transurethral resection of the prostate (TURP) is still representing the gold standard [2]. On the other hand the surgical approach is changing from conventional monopolar TURP to minimally invasive surgical techniques such as holmium laser enucleation (HoLep) or GreenLight lithium borate laser vaporization (PVP) [1] or other minimal invasive techniques. Transurethral enucleation of the prostate (TUEP) has been available as a monopolar current-based enucleation—resection since it was first described by Hiraoka in 1983 [3]. Although it was the blueprint for all other transurethral enucleations to come, it remained a local phenomenon in Japan [4]. Only when enucleation was in focus again with laser technology and the mechanical tissue morcellator, did it come into focus after publication of a paper on holmium laser enucleation of the prostate (HoLEP) in 1998 by Fraundorfer and Gilling [5]. HoLEP is regarded as a standard approach for the treatment of large prostate glands, and the great evidence base is mentioned in support of that. However, only in 2006 there was the first randomized controlled trial on HoLEP versus bipolar enucleation (plasmakinetic enucleation of the prostate, PKEP) published by the same group [6].

Nowadays 15 randomized controlled trials have been published comparing bipolar enucleation with a standard treatment arm (OP or TURP) so far. Numerous studies have demonstrated that bipolar TUEP is an attractive minimally invasive alternative to OP for large BPH, with comparable functional results and significantly lower perioperative morbidity [7-12]. Recently [name] introduced a specific electrode which aims to reproduce a wedge to more easily perform anatomic enucleation of the prostate. This technique propagated by its inventor is known as BipolEP.

1. 2 The need for a trial

There is no doubt that BipolEP has huge potentials. BipolEP has shown to be performed effectively and safely with functional outcomes and complications similar to the gold standard for prostatic enlargement, whereas it has the advantages of a shorter catheter period, shorter hospital stays and less blood transfusion compared to open surgery [13].

To the best of our knowledge there is not a randomized trial available compared this new device with TURP. For this reason this trial is needed

- 3. Hiraoka Y: A new method of prostatectomy, transurethral detachment and resection of benign prostatic hyperplasia. *Nihon Ika Daigaku zasshi* (1983) **50**(6):896-898.
- 5. Fraundorfer MR, Gilling PJ: **Holmium:Yag laser enucleation of the prostate combined with mechanical morcellation: Preliminary results.** *European urology* (1998) **33**(1):69-72.

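### The 12-month IPSS test makes no use of baseline IPSS: a modest, inexpensive gain in efficiency is missed, but validity is not affected

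*Combined protocol and SAP*

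**What the plan says.** All references are to the combined protocol and SAP.

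- **Endpoint.** The Concept part of the statistical section states "Two primary endpoints are chosen: (1): IPSS after 12 month". The Outcome(s) row names the endpoint differently, as "IPSS improvement at 12 months", which suggests a change from baseline.
- **Test.** Under Group Comparisons, Primary Endpoint (1), the hypotheses "will be investigated either by a parametric or by a non-parametric one-sided test of equivalence", at "type I error = 5% one-sided" and with "non-inferiority range = 3". A normality check, on log-transformed data if appropriate, decides between the two forms. No covariate, ANCOVA or repeated-measures model appears anywhere.
- **IPSS data.** Entry requires "I-PSS greater than 15", so a baseline score is obtained. Follow-up includes "I-PSS, QOL, Qmax and PVR (at 1, 4 and 12 months".
- **Allocation.** Minimisation uses prostate volume and catheter status only.
- **Analysis sets.** The per-protocol (PP) set holds men without any drop-out event, and it takes precedence. In the ITT set, a missing 12-month score is replaced by the worst value seen in the study.

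**The concern.** Baseline IPSS is the obvious candidate predictor of 12-month IPSS, and the trial has it already. Leaving it out has two consequences. The standard error of the arm difference is larger than it need be. And because neither allocation nor analysis deals with baseline IPSS, a chance difference between arms passes in part into the 12-month difference that is compared with 3.

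The arms are small (42 enrolled, about 33 expected to complete), and the result of endpoint (1) decides whether endpoint (2) is tested at all. It is therefore worth asking how much is lost.

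**Working it through.** **Inputs from the documents.** Margin 3; SD 4 in both groups; expected mean 4 in both groups, so true difference 0; one-sided alpha 5%; power 90%; 31 evaluable per group; 42 enrolled per group; drop-out 20%.

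**Assumed input.** Correlation r between baseline and 12-month IPSS. The documents give none, so r is varied from 0.1 to 0.4.

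**1. The plan's own figure.** n = 2 × SD² × (1.645 + 1.282)² / margin² = 2 × 16 × 8.564 / 9 = 30.45, rounded up to 31. The plan's 31 is reproduced. Exact power (non-central t) at 31 is 89.9%.

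**2. Expected completers.** 42 × 0.80 = 33.6, taken as 33 per arm. Unadjusted standard error = 4 × √(2/33) = 0.985, and exact power is 91.5%.

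**3. With baseline adjustment.** Residual SD = 4 × √(1 − r²). The equivalent number of unadjusted men per arm is 33/(1 − r²).

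| r | Residual SD | Standard error, n = 33 | Power | Equivalent n per arm |
|---|---|---|---|---|
| 0 (planned) | 4.000 | 0.985 | 91.5% | 33.0 |
| 0.1 | 3.980 | 0.980 | 91.7% | 33.3 |
| 0.2 | 3.919 | 0.965 | 92.4% | 34.4 |
| 0.3 | 3.816 | 0.939 | 93.5% | 36.3 |
| 0.4 | 3.666 | 0.903 | 95.0% | 39.3 |

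The table leaves out the small cost of estimating the slope, about 1/(2 × 33 − 4) = 1.6% of the variance. That cancels the 1% gain at r = 0.1 but not the 4% to 16% gains at r = 0.2 to 0.4.

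**4. Effect of a chance baseline imbalance.** An imbalance of z standard errors shifts the expected 12-month difference by r × 0.985 × z; the baseline SD cancels. At r = 0.3 and z = 1 the shift is 0.295 points, about 10% of the margin. The unadjusted test claims non-inferiority if the observed difference is below 3 − 1.669 × 0.985 = 3 − 1.643. The following uses a normal approximation with conditional standard error 0.939.

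- Imbalance against BipolEP, no true difference: (3 − 1.643 − 0.295)/0.939 = 1.13, so conditional power is about 87%.
- Imbalance in favour of BipolEP, true difference at the margin: (−1.643 + 0.295)/0.939 = −1.44, so the conditional false-claim rate is about 7.6%.
- At z = 2 the two figures are about 79% and 13%.

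These are conditional figures. Averaged over all possible imbalances, the test keeps its nominal 5%.

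**5. Score or change.** Suppose change = a + b × arm + c × baseline. Adding baseline to both sides gives score = a + b × arm + (c + 1) × baseline, with the same b. With baseline in the model, score and change therefore give one arm difference (improvement only reverses the sign). Without it they are different tests. If the two SDs are equal (assumed) and r = 0.3, the change has SD 4 × √(2 × 0.7) = 4.733. By the normal approximation, power at 31 per arm is then about 80%, against about 90% for the score.

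**6. Months 1 and 4.** For men with a 12-month score, a repeated-measures model with baseline and all visits (33.6 per group, r = 0.3) gives a standard error of 0.931 for the 12-month contrast, with or without months 1 and 4. Early visits help only through men who miss month 12, and those men fall outside the PP set.

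**The case against.** The strongest reply is that nothing here is wrong. The unadjusted comparison is a legitimate test, and the plan reaches its stated power on its own inputs. Chance imbalance is already part of the unadjusted standard error and is covered by the 5% error rate. The gain depends on a correlation the documents do not supply, and the entry threshold on IPSS narrows the baseline range and may weaken it. At 0.2 the gain is worth 34.4 − 33 = 1.4 men per arm; at 0.1 it is effectively nil. All of this stands. What remains is that, for the trial actually run, adjustment makes the decision insensitive to baseline imbalance, at no cost in data.

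Two stronger readings are tempting and are not supported.

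- **The test is biased or underpowered.** A reader might infer this from the missing adjustment. Allocation does not depend on baseline IPSS, so the unadjusted difference is unbiased on average in that respect, and step 2 shows adequate power.
- **Valuable early data are thrown away.** A reader might infer that modelling months 1 and 4 would markedly enlarge the effective sample. In the PP analysis they add essentially nothing. Any gain from incomplete men requires a different analysis set and an assumed pattern of drop-out timing, which the documents do not give. Nor are the early scores wholly unused: the plan compares other variables between groups, though only descriptively.

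The plan's log and non-parametric options also respond to a real feature: a mean of 4 with SD 4 on a score that cannot fall below zero implies skewness. A replacement method must deal with that.

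**Conclusion.** The point holds as a missed efficiency gain. At about 33 completers per arm, baseline adjustment would raise power from 91.5% to between 91.7% and 95.0% for an assumed correlation of 0.1 to 0.4, with no practical benefit at the bottom of that range. It would also remove the dependence of the non-inferiority decision on chance baseline imbalance. These figures rest on the plan's SD of 4, a true difference of zero, and a linear relation between baseline and 12-month IPSS. Validity and the planned sample size are not in question.

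The two names for the endpoint, improvement and 12-month score, do conflict. Under ANCOVA the conflict no longer affects the test, but the wording must still be reconciled.

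**What to change.** Amend the SAP before the data are analysed:

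1. Define the primary estimate for endpoint (1) as the arm difference in 12-month IPSS from an ANCOVA on baseline IPSS, prostate volume and catheter status. Compare its upper one-sided 95% confidence limit with 3 on the raw score scale. Let this replace the choice of test by normality check.
2. Specify a robust or bootstrap interval for use if residuals are skewed.
3. State how a missing baseline score is handled, for example in men who enter in retention, whose baseline IPSS the documents do not describe. Mean imputation with a missing-score indicator is suitable. Catheter status alone would serve only if missing scores coincided exactly with catheterisation, which the documents do not say.
4. Enter prostate volume as a continuous variable or in categories that cover the whole entry range. The listed minimisation strata start at 60 ml, while entry starts at 40 ml.
5. Use one definition of endpoint (1) throughout.
6. If the 1- and 4-month scores are to be used, do so in a likelihood-based repeated-measures model for the ITT analysis, where it would be an alternative to worst-value replacement.

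The cost is SAP wording and a standard model. No extra patients, visits or data are needed.

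### Allocation is minimised on prostate volume and catheter status, but neither primary analysis adjusts for them; if they are prognostic, the parametric test is valid but conservative and loses some precision.

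*Combined protocol and SAP*

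**What the plan says.** - **Allocation:** "For the allocation of treatment to subjects the minimization method will be used (manual see accompanying documents". The factors are volume, "prostate 60 to 80 ml / more than 80 ml", and catheterised or not. The procedure is run centrally by the coordinating centre.
- **Primary endpoint (1), 12-month IPSS:** after a normality check at the 10% level, the hypotheses "will be investigated either by a parametric or by a non-parametric one-sided test of equivalence", with a range of 3 points and 5% one-sided error.
- **Primary endpoint (2), tissue resection in g/min:** after the same check, "Hypotheses will be investigated either by the t-test for independent samples or by the Mann-Whitney U-test", at 2.5% one-sided and only if endpoint (1) succeeds.
- **Sample size:** based on endpoint (1) alone and a parametric test, with "IPSS after 12 months in both groups (Mw ± SD) = 4 ± 4". It gives 31 per group, raised to 42: "Assuming a drop-out rate of 20% and considering the possible need for a non-parametric test".
- **Populations:** "The PP analysis is paramount". Missing primary values are replaced in the ITT set only, by the worst value in the study.

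No covariate, stratified analysis or re-randomisation test is named for either primary endpoint. All other variables get univariate comparisons.

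**The concern.** Minimisation removes most of the chance imbalance between arms on volume and catheter status. The two-sample standard error still counts the outcome variation due to those factors as if it could differ freely between arms. If the factors predict the outcome, the standard error is too large, the confidence interval too wide and the true type I error below nominal.

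What is at stake is precision. Endpoint (2) is the more exposed, because the sample size was not set for it. Both factors must be known to allocate a patient, so adjustment needs no new data. It does have to be specified in advance: under Post-hoc Analyses, anything added later is only descriptive.

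**Working it through.** **1. The plan's own figure.** Inputs from Sample Size Justification: margin 3, SD 4, true difference 0, one-sided error 5%, power 90%.

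n = 2 × (1.645 + 1.282)² × 4² / 3² = 30.4, so 31 per group, as stated. Exact noncentral-t power at 31 is 89.9%.

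With 20% drop-out, 42 × 0.8 = 33.6, so about 33 per group are evaluable. Then SE = 4 × √(2/33) = 0.985, noncentrality = 3/0.985 = 3.05, df = 64, power 91.5%. The planned 90% is met without adjustment.

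**2. Cost of adjusting if the factors explain nothing.** With k = 2 covariates, SE = SD × √[(2/n)(1 − R2)(2n − 3)/(2n − 3 − k)] and df = 2n − 2 − k.

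- Endpoint (1), n = 33, R2 = 0: SE = 0.985 × √(63/61) = 1.001, noncentrality 3.00, df = 62, power 90.7%. Loss: 91.5 − 90.7 = 0.8 points.
- Endpoint (2), n = 33, assumed effect 0.6 SD, 2.5% one-sided: 67.0% unadjusted, 65.6% adjusted. Loss: 1.4 points. Losses at 0.5 and 0.8 SD are no larger (51.6 to 50.3%; 89.3 to 88.3%).
- Break-even R2 is about 0.03 for both endpoints.

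**3. Conservatism of the unadjusted test.** Under near-perfect balance, true error ≈ 1 − Φ(z/√(1 − R2)). At R2 = 0.10 and 0.20 this gives 4.1% and 3.3% for endpoint (1), and 1.9% and 1.4% for endpoint (2). Drop-out and imperfect balance soften this, so it was also simulated.

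**4. Simulation.** Assumed, because the documents do not give them: normal outcomes, 40% of men above 80 ml, 30% catheterised, R2 split equally between the factors, assignment probability 0.8 or 1.0 (the minimisation manual is a separate document), and men at 40–60 ml placed in the lower stratum. There were 84 men, 20% random drop-out and 20,000 runs per setting. The model has arm, continuous volume and catheter status. Endpoint (2) power is at 0.6 SD. Ranges span the settings.

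| R2 | Endpoint (1) power, unadjusted v adjusted | Endpoint (2) power, unadjusted v adjusted | Unadjusted type I error, (1) / (2) |
|---|---|---|---|
| 0 | 91.5–91.7 v 91.3–91.5% | 68 v 67% | – |
| 0.10 | 92.0–92.6 v 93.3–93.9% | 68–69 v 71–72% | 4.3–4.4 / 2.2–2.3% |
| 0.20 | 92.8–93.4 v 95.2–95.8% | 69 v 76–77% | 3.7–3.9 / 1.8–1.9% |

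The adjusted model's error was 4.8–5.0% and 2.4–2.7%, close to nominal. A repeat simulation at R2 = 0.20 gave 93.2 v 95.6% for endpoint (1) and 68.4 v 77.1% for endpoint (2), with unadjusted errors of 3.7% and 1.6%.

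**5. The non-parametric branch.** A non-negative score with mean 4 and SD 4 is probably skewed. With an assumed negative binomial of that mean and SD, the raw-scale normality check failed in over 99% of runs. With equal shapes in both arms, Mann-Whitney power was 98.4–98.7%. The linear model had 91.2–93.1% across factor R2 of 0 to 0.13; a repeat run gave 98.4 v 90.9%.

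**The case against.** The strongest counter-argument is that the t-test may seldom be used for endpoint (1). Under three assumed non-negative shapes with mean and SD near 4, raw-scale normality failed in at least one arm in 98.9–99.9% of runs. Raw and logged data both failed in 78–99%. On the rank branch, a linear model can cost several points of power. **This stands**, and it limits the fix to the parametric branch. The rank test's advantage assumes equal shapes in both arms; how it behaves otherwise is a separate matter from the omitted factors.

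It is also fair that the endpoint (1) gain is small and that the endpoint (2) gain rests on an assumed R2 and effect size. The synopsis itself calls tissue resection a key secondary endpoint in one place and a primary endpoint in another. These points stand and make the change optional. They do not remove it, since the downside is smaller still.

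A reader might infer more than the documents support:
- **That the planned test is invalid or inflates false non-inferiority claims.** The error runs the other way: the true rate is at or below nominal.
- **That endpoint (1) is underpowered without adjustment.** It has 91.5% at 33 per group.
- **That both planned tests should give way to a linear model throughout.** Omitted minimisation factors are no reason to displace the rank test, and doing so could lose power.
- **That the two factors are known to be prognostic.** Their use in allocation suggests the sponsor thought them important, but no figure is given.

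**Conclusion.** The mismatch between allocation and analysis is real, and its consequence is lost precision on the parametric branch. At an assumed R2 of 0.10–0.20 the loss is about 1–2.5 points of power for endpoint (1) and about 3–9 points for endpoint (2) at 0.6 SD. If R2 is near zero there is no loss. Confidence is medium, because R2, the endpoint (2) effect, factor prevalence and the random element of the minimisation are all assumed.

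The power figures describe a per-protocol analysis with random drop-out. They do not carry over to the planned ITT analysis, because the worst-case replacement rule was not modelled. How far minimisation makes the rank test conservative was not quantified either.

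**What to change.** Before analysis, state the following for both analysis populations, leaving the missing-value rules, margin, error levels and gatekeeping order as they are.

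1. Where the parametric branch applies, replace the two-sample t-test by a linear model with arm, TRUS volume (continuous) and catheter status.
   - Endpoint (1): compare the one-sided 95% upper bound of the adjusted IPSS difference (BipolEP minus TURP) with 3 points, on the original scale.
   - Endpoint (2): test the arm effect at 2.5% one-sided, only after endpoint (1) succeeds.
   - Keep the unadjusted t-test as a sensitivity analysis.
2. Where the non-parametric branch applies, keep the planned rank test as primary and report the adjusted model as a prespecified sensitivity analysis.

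The cost is a few sentences of analysis text and no new data, plus the small power loss shown in step 2 of the working if the factors explain nothing; endpoint (1) stays above 90%.

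Separately, the lower volume stratum starts at 60 ml while eligibility starts at 40 ml. The two passages must be reconciled, because as written an eligible man below 60 ml has no stratum.

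### Non-primary outcomes with a pre-operative value, hemoglobin above all, get unadjusted two-sample tests; ANCOVA would tighten these descriptive estimates at almost no cost

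*Combined protocol and SAP*

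**What the plan says.** The Further Variables paragraph under Statistical Methods is the only analysis rule for non-primary outcomes: "All other variables will be analysed by usual parametric and non-parametric tests for univariate comparisons of independent samples". No ANCOVA, regression model or covariate appears anywhere in the document.

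The synopsis shows which of these outcomes have a pre-operative value:

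- Hemoglobin. The safety outcomes include "Blood loss (hemoglobin prior and postoperative"; the entry does not say which quantity is compared between arms.
- QOL and Qmax. The eligibility criteria read "I-PSS greater than 15 QOL score 3 or greater Qmax less than 15 ml per second or patients with acute urinary retention", so both are assessed before surgery, except that a man in retention may have no Qmax.
- Prostate volume. Eligibility requires "Prostate size on preoperative TRUS of 40 to 150 ml", and TRUS is repeated at 4 months.

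The follow-up schedule lists "I-PSS, QOL, Qmax and PVR (at 1, 4 and 12 months" and "IIEF-15 and PSA (at 4 and 12 months". It mentions no baseline PVR, IIEF-15 or PSA, so those outcomes are left out of this point.

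On the status of these results, the plan says that, apart from the hypothesis tests, "the results of inferential statistics will be descriptive only". It adds: "For selected variables, two-sided 95% confidence intervals will be calculated".

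**The concern.** A two-sample test has no place for a covariate. It can compare the follow-up value, which leaves the pre-operative value unused, or the change, which gives that value a fixed weight of one. ANCOVA estimates the weight from the data. Under randomisation all three approaches target the same arm difference, so the choice is one of precision.

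Precision is scarce here. The trial was sized only for 12-month IPSS, and nothing was planned for hemoglobin, QOL, Qmax or TRUS volume. What these outcomes contribute is an estimate and its interval, and an interval wider than it need be says less about safety and function.

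For hemoglobin there is a second gap. Because the compared quantity is not fixed, the choice between postoperative value and drop could be made after the data are seen, and the two can give different answers.

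**Working it through.** **Sample size available.** Inputs from Sample Size Justification: margin 3, SD 4, true difference 0, one-sided 5%, power 90%.

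n per group = 2 × 4² × (1.645 + 1.282)² / 3² = 32 × 8.567 / 9 = 30.5, rounded up to 31. This matches the plan. With an assumed rank-test efficiency of 3/π = 0.955 (the plan gives no figure), 31/0.955 rounds up to 33, and 33/0.8 rounds up to 42 per group, or 84 in total. This matches too. Neither figure is disputed. They give N = 84 with complete data and N = 62 with only the required evaluable cases.

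**Variance of the arm difference.** Let σ be a common SD before and after surgery, r the pre/post correlation and n the number per arm:

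- postoperative value alone: 2σ²/n
- drop: (2σ²/n) × 2(1 − r)
- ANCOVA: (2σ²/n) × (1 − r²), before a small penalty for estimating the slope

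Hence postoperative/ANCOVA = 1/(1 − r²), and drop/ANCOVA = 2(1 − r)/[(1 − r)(1 + r)] = 2/(1 + r).

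**Hemoglobin.** The documents give no r; 0.6 to 0.8 is an assumption.

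| r | postoperative / ANCOVA | drop / ANCOVA | ANCOVA interval width relative to drop |
|---|---|---|---|
| 0.6 | 1/0.64 = 1.56 | 2/1.6 = 1.25 | 1/√1.25 = 0.89 |
| 0.7 | 1/0.51 = 1.96 | 2/1.7 = 1.18 | 1/√1.18 = 0.92 |
| 0.8 | 1/0.36 = 2.78 | 2/1.8 = 1.11 | 1/√1.11 = 0.95 |

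**Cost of the slope.** The ANCOVA variance is multiplied by about 1 + 1/(N − 4). At N = 84 this is 1 + 1/80 = 1.0125; at N = 62 it is 1 + 1/58 = 1.017. So at r = 0 ANCOVA loses about 1% (N = 84) or 2% (N = 62) in variance against the postoperative value. At N = 84 it breaks even where (1 − r²) × 1.0125 = 1, that is at r of about 0.11.

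With this penalty, the half-widths of the 95% interval at N = 84, in SD units, are:

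| r | postoperative | drop | ANCOVA |
|---|---|---|---|
| 0.6 | 0.434 | 0.388 | 0.350 |
| 0.7 | 0.434 | 0.336 | 0.312 |
| 0.8 | 0.434 | 0.275 | 0.262 |

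Against the drop, the ratios are 0.350/0.388 = 0.90, 0.312/0.336 = 0.93 and 0.262/0.275 = 0.95. The penalty barely changes the result.

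**The open choice for hemoglobin.** The drop is more precise than the postoperative value only when 2(1 − r) < 1, that is r > 0.5. ANCOVA avoids the choice, because regressing either the postoperative value or the drop on the pre-operative value gives the same adjusted arm difference.

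**QOL, Qmax and TRUS volume.** No r is given, and entry cut-offs may lower it. At N = 62 the half-width for the follow-up value alone is 0.508 SD. With ANCOVA it is 0.513 (r = 0), 0.489 (r = 0.3), 0.444 (r = 0.5) or 0.366 (r = 0.7). These figures show the possible range and do not predict the gain.

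All formulas describe the parametric comparison. The plan's rank tests take no covariate either.

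**The case against.** The strongest reply is that blood loss described by hemoglobin before and after surgery most naturally means the drop, since a postoperative value alone does not measure loss. A t-test or Mann-Whitney test on the drop fits the plan's wording and already uses the pre-operative value. This stands. A reader might infer that the planned tests ignore the baseline and that ANCOVA is therefore worth 56 to 178% more patients. The documents do not support that: the figure belongs to the less plausible reading.

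Second, these results are declared descriptive and the unadjusted comparison is unbiased, so ANCOVA is only an efficiency preference. It is true that no hypothesis, margin or power target is touched. But descriptive results are judged by estimate and interval, and the plan promises intervals for selected variables, so the gain in precision remains.

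Third, adjustment is not free for the functional outcomes. Men in retention may have no baseline Qmax, and restricting the comparison to men who have one would discard follow-up data that the present plan uses. QOL has an entry floor of 3, and Qmax is capped below 15 ml/s outside retention. Such restriction can lower the correlation and shrink the gain. This stands too, and the recommendation for Qmax allows for it.

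**Conclusion.** The point holds as one about precision. The plan leaves pre-operative information out of the models for its non-primary outcomes and does not fix the quantity compared for hemoglobin. If the drop is analysed, its variance is 1.11 to 1.25 times that of ANCOVA, and ANCOVA's interval would be about 5 to 11% narrower. If the postoperative value alone is analysed, the ratio is 1.56 to 2.78. Both ranges assume equal pre- and postoperative variances and a correlation of 0.6 to 0.8. For QOL, Qmax and TRUS volume the gain cannot be sized from the documents and may be small.

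Three stronger inferences are not supported:

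- That a real safety difference would be hidden. On the likely reading the interval changes by a tenth or less, and adverse events and Clavien-Dindo complications have no baseline to adjust for. Among the safety outcomes only hemoglobin is affected.
- That the confirmatory conclusions are at risk. The two primary endpoints have their own tests, which this point leaves alone.
- That transfusions bias the hemoglobin comparison. The documents give no transfusion rate, transfusion rule or sampling time, and they mention transfusion only in a comparison with open surgery. The question is also separate from whether to adjust.

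**What to change.** Replace the univariate rule for the outcomes that have a pre-operative value:

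- Analyse postoperative hemoglobin by ANCOVA on pre-operative hemoglobin, and state this as the definition of the blood-loss comparison.
- Analyse QOL and 4-month TRUS volume in the same way on their pre-operative values.
- For Qmax, use the adjusted analysis in men with a baseline value and keep the unadjusted comparison in all men, so that retention patients are not lost.
- Report the adjusted arm differences with two-sided 95% confidence intervals, still labelled descriptive.

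The other non-primary outcomes can stay under the present rule.

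The cost is a few sentences of SAP text, one degree of freedom per model (about 1% in variance at N = 84 if the correlation is near zero) and the need for complete baselines. No new measurement is required: pre-operative hemoglobin is a listed item, and the other values are needed for eligibility. The data-collection form should carry the values themselves, since a tick that the criterion was met would not be enough.
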